6.6.2 Procedural Characteristics

- Surgical site (indication for product usage): primary organ involved in the index procedure as defined by the primary procedure code (See [Table A- 1](#)).
 - Rectum
 - Sigmoid
 - Descending colon
 - others
- Primary diagnosis: Primary ICD-10-CM discharge diagnosis code recorded during the index hospital admission will be used to designate indication for surgery (See [Table A- 5](#)).
 - Malignant neoplasms
 - Benign neoplasm

RWE23-SAF-001:Comparative safety study to assess the risk of AL of 2-row vs 3-row circular staplers

- Diverticular disease or Diverticulitis
 - Intestinal obstruction
 - Others
- Diverting stoma (yes, no) occurred prior to or on the same day as the index procedure (i.e., left-sided colorectal surgery) during the index admission: defined as the presence of an ICD-10-PCS procedure code indicating diverting stoma (see [Table A- 3](#)) identified prior to or on the same day as the index procedure during the index admission
 - Surgical approach:
 - Open
 - Laparoscopic
 - Robotic assisted
 - Unknown

Surgical approach is determined by the primary and secondary procedure code. For a *primary* procedure code in ICD-10-PCS, the fifth character of the code explicitly identifies the surgical approach with '0' standing for an open procedure and characters other than '0' representing a laparoscopic approach, unless the presence of a *secondary* procedure code (i.e., ICD-10-PCS: 8E0W%CZ—Robotic Assisted Procedure of Trunk Region) indicating a robotic assistance procedure. Conversions from laparoscopic or unknown surgical approach to open surgical approach will be categorized as open surgery (the procedure code list for conversions is provided in [Table A- 6](#)).

- Year of index procedure
- Admission type during index procedure (elective admission; emergent or urgent admission): elective surgery was scheduled in advance, while urgent or emergency surgery was done because of an urgent medical condition. We assume an index encounter categorized as elective indicates a procedure scheduled in advance, while urgent or emergency index encounter admissions reflect an urgent medical condition.

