4. RATIONALE AND BACKGROUND

Anastomotic leak (AL) after colorectal surgery is a serious complication, and can result in intra-abdominal abscess, wound infection, bowel obstruction, rupture of the operation wound, or require reoperation.¹⁻⁴ Male sex, low anterior resection, and patient comorbidity including malnutrition, obesity (body mass index >30 kg/m²), and diabetes, are widely reported risk factors for AL.⁵⁻⁸

The use of circular stapling devices to facilitate colorectal anastomosis has been demonstrated to reduce the risk of AL vs hand sewn sutures and is widely used in colorectal anastomosis after left-sided colorectal surgery. Many circular staplers are characterized by two rows of staples fired under manual grip force, aimed to guarantee a high anastomotic resistance with reduced tissue damage. Among them are Ethicon manual circular staplers and Medtronic EEA™ Circular Stapler with DST Series™ Technology (device variants described in Table 1).

Technological advancements led to the introduction of the Tri-staple™ Technology of manual staplers in the US Market in 2018 (Medtronic EEA™ circular stapler with Tri-Staple™ technology), which includes three staple lines and is thought to guarantee a higher resistance of the anastomotic site with less stress on tissue as compared to the two-row circular staplers.⁹⁻¹¹ Based on the results of two 2022 publications, 2-row manual circular staplers, including Ethicon manual circular staplers and Medtronic EEA™ Circular Stapler with DST Series™ Technology, may have a higher risk of AL, when compared to the Medtronic EEA™ circular stapler with Tri-Staple™ technology (3-row manual circular staplers).^{8, 12} This evidence was reported from single-center retrospective studies conducted in Italy and Japan. Such settings have the potential for selection bias, and the estimates of AL risks are limited by the small sample size included in both studies and the variations in the diagnosis consensus to ascertain AL cases. A comparative analysis of the risk of AL among two-row versus three-row manual circular staplers in colorectal anastomosis using a nationally representative database has not been fully examined or demonstrated in the United States (US).

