6.3 Sample Selection

Inclusion Criteria

Patients who meet all of the following criteria will be included in this study:

- 1) Billing charges for a study device (Ethicon Manual Circular Stapler, Medtronic EEA™ Circular Stapler with DST Series™ Technology, or Medtronic EEA™ Circular Stapler with Tri-Staple™ Technology) between January 1, 2019, and June 30, 2022 (or latest available data)
- 2) Undergoing a left-sided colorectal surgery (i.e., the index procedure), defined as presence of a qualifying procedure code for left-sided colorectal surgery (see [Table A-1](#))
- 3) Aged 18 years or older at the index procedure.

Exclusion Criteria

Patients who meet any of the following criteria will be excluded:

- 1) Patient encounters where more than one study device (Ethicon Manual Circular Stapler, Medtronic EEA™ Circular Stapler with DST Series™ Technology, or Medtronic EEA™ Circular Stapler with Tri-Staple™ Technology) was used in the same index procedure
- 2) Missing patient age or sex
- 3) Presence of an admission diagnosis indicating anastomotic leak (See ICD-10-CM in the [Table A-2](#)) during the index admission noted as present on admission*

*Present on admission will be identified with “Yes” in the present on admission field in the PHD.

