6.9.2 Primary Comparative analysis

The goals of comparative analyses are to: 1) estimate the RR of AL for Ethicon Manual Circular Staplers compared to Medtronic EEA™ Circular Stapler with Tri-Staple™ Technology; 2) estimate the RR of AL for the Medtronic EEA™ Circular Stapler with DST Series™ Technology compared to Medtronic EEA™ Circular Stapler with Tri-Staple™.

The primary analyses will be conducted separately for the comparison between Ethicon Manual Circular Stapler versus Medtronic EEA™ Circular Stapler with Tri-Staple™ Technology and the comparison between Medtronic EEA™ Circular Stapler with DST™ Technology and Medtronic EEA™ Circular Stapler with Tri-Staple™ Technology. See the expected outputs in [Table B- 7](#) and [Table B- 8](#).

A propensity score weighting (PSW) method will be used to control for potential confounders by balancing the distribution of baseline demographic, clinical, and procedural characteristics between the comparison groups. The following baseline variables will be considered in the propensity score model based on their clinical relevance to the safety of the device: patient demographics (age, sex, and race), clinical characteristics (CCI, comorbid conditions, diverting stoma occurred prior to or on the same day as the index procedure), procedural characteristics (procedure year, surgical site, primary diagnosis, surgical approach, and admission type), and hospital and provider

RWE23-SAF-001:Comparative safety study to assess the risk of AL of 2-row vs 3-row circular staplers

characteristics (hospital region, hospital location, hospital setting, hospital bed size, and surgeon specialty).

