APPENDIX A: DIAGOSIS AND PROCEDURE CODES

Table A- 1: Procedure Codes (ICD-10-PCS) for Left-sided Colorectal Surgery

CODE	CODE DESCRIPTION
ODTG%	Resection, large intestine, left
ODTM%	Resection, Descending Colon
ODTN%	Resection, Sigmoid Colon
ODTP%	Resection, Rectum
ODBG%	Excision, large intestine, left
ODBM%	Excision, Descending Colon
ODBN%	Excision, Sigmoid Colon
ODBP%	Excision, Rectum
ODQM%	Repair, Descending Colon
ODQN%	Repair, Sigmoid Colon
ODQP%	Repair, Rectum

'%' at the end of the code denotes any value for subsequent characters.

'%' in the middle of the code denotes any valid value for a character in that specific position

RWE23-SAF-001:Comparative safety study to assess the risk of AL of 2-row vs 3-row circular staplers

Table A- 2: Diagnosis Codes (ICD-10-CM) Indicating Anastomotic Leak

CODE	CODE DESCRIPTION
K63.2	Fistula of intestine
K65.0	Generalized Peritonitis
K65.1	Peritoneal abscess
K91.89	Other postprocedural complications and disorders of digestive system
Y83.2	Surgical operation with anastomosis, bypass or graft as the cause of abnormal reaction of the patient, or of later complication, without mention of misadventure at the time of the procedure

Table A- 3: Procedure Codes (ICD-10-PCS) for Diverting Stoma

CODE	CODE DESCRIPTION
0D18%%4	Bypass Small Intestine to Cutaneous
0D1B%%4	Bypass Ileum to Cutaneous
0D1E%%4	Bypass large intestine to Cutaneous
0D1H%%4	Bypass Cecum to Cutaneous
0D1K%%4	Bypass Ascending Colon to Cutaneous,
0D1L%%4	Bypass Transverse Colon to Cutaneous
0D1M%%4	Bypass Descending Colon to Cutaneous
0D1N%%4	Bypass Sigmoid Colon to Cutaneous

'%' in the middle of the code denotes any valid value for a character in that specific position

RWE23-SAF-001:Comparative safety study to assess the risk of AL of 2-row vs 3-row circular staplers

Table A- 4: Diagnosis Codes (ICD-10-CM) for Comorbid Conditions

Comorbid conditions	CODE	DESCRIPTION
Alcohol dependency	F10.2%	Alcohol dependence
Cardiovascular diseases	G45%, G46%, I60%, I61%, I62%, I63%, , I65%, I66%, I67%, I68%, I69%, H34.0%	cerebrovascular disease
	I43, I50%, I09.9, I11.0, I13.0, I13.2, I42.0, I42.5, I42.6, I42.7, I42.8, I42.9	congestive heart failure
	I20%, I23%, I24%, I25%	ischemic heart disease
	I21%, I22%	myocardial infarction
	I70%, I71%, I73.1, I73.8%, I73.9, I77.1, Z95.8%, Z95.9	peripheral artery disease
Chronic obstructive pulmonary disease	J44.0, J44.1, J44.9	Chronic obstructive pulmonary disease

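### Patients enter on any Table A-1 code, but site and open/laparoscopic approach come from the primary code and operation type is not modelled, so adjustment for level and extent of surgery is weaker than the codes allow

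*Supplement*

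**What the plan says.** - **Entry.** Protocol section 6.3 requires a study-device charge and a left-sided colorectal operation, "defined as presence of a qualifying procedure code for left-sided colorectal surgery". The code does not have to be the primary one.
- **Site.** Section 6.6.2 uses four levels (rectum, sigmoid, descending colon, others), set by the "primary organ involved in the index procedure as defined by the primary procedure code", with a pointer to Table A-1. Section 8 describes the source as the primary procedure codes of the index hospitalization, without tying them to the index date.
- **Approach.** Section 6.6.2 reads open versus laparoscopic from the fifth character of the primary code. A secondary robotic code and the Table A-6 conversion codes can change the result.
- **Operation type.** Table A-1 lists both "Resection, Rectum" and "Repair, Rectum", with excision codes as well, and does the same for sigmoid and descending colon.
- **Propensity model.** Section 6.9.2 includes site and approach, but no variable for resection, excision or repair.
- **Stated risk factors.** Section 4 opens its list of widely reported risk factors for leak with "Male sex, low anterior resection, and patient comorbidity".

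**The concern.** The entry rule and the site rule use different codes, and nothing reconciles them. Where they disagree, the record may hold a rectal code that the adjustment never uses. Where they agree, the Rectum level still treats a full resection and a repair as exchangeable. The diagnosis covariate does not recover the difference, because Table A-5 places rectal cancer in one category with colon cancer.

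Two outputs are exposed. The first is the adjusted RR: if the devices are used on different mixes of operations, weighting on a misfiled site leaves part of that confounding in place. The second is primary objective 1, which reports leak incidence by patient characteristics. Table B-6 has rows for surgical site, and a misfiled site distorts those rows whether or not case mix differs between devices.

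**Working it through.** **1. The rules applied to four patients, read literally**

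| Codes on record | Enters? | Recorded site |
|---|---|---|
| Primary sigmoid resection, secondary rectal resection | Yes | Sigmoid |
| Primary code outside Table A-1, secondary rectal resection | Yes | Others; approach comes from the other operation |
| Primary rectal resection | Yes | Rectum |
| Primary rectal repair | Yes | Rectum |

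The first two lose a rectal site that is in the data. The last two are indistinguishable on site.

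**2. Whether the plan's safeguards would catch this**
- Balance (section 6.9.2) is judged by standardized differences on the recorded variables. Recorded site can balance while true site does not.
- The rule that adds an unbalanced variable to the outcome model reaches only variables already in the propensity model, so operation type cannot enter.
- Section 8 accepts that site may be misclassified and expects the error to be non-differential. Non-differential error in a confounder still leaves residual confounding, in either direction.

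**3. The plan's own figures**

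Table 2 is the only statistical calculation in the plan. Its second row (risks 0.03 and 0.06, n = 500 and 6,000, one-sided 0.025) reproduces:
- Pooled risk = (15 + 360)/6,500 = 0.0577, null SE 0.01085, alternative SE 0.00822.
- Power = Φ[(0.03 − 1.96 × 0.01085)/0.00822] = Φ(1.06) = 0.856.

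The other five rows also reproduce. None bears on this point.

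**4. Illustration A: a residual difference in share**

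All inputs are assumed; the documents give none of them. Take a leak risk ratio R = 2.5 for rectal resection, a true device RR of 1, and shares q_T (target) and q_C (comparator) that still differ after weighting.

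Apparent RR = (1 + 1.5 q_T)/(1 + 1.5 q_C)
- 0.30 vs 0.35: 1.45/1.525 = 0.951
- 0.25 vs 0.35: 1.375/1.525 = 0.902
- Shares reversed: 1.525/1.45 = 1.052 and 1.525/1.375 = 1.109

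**5. Illustration B: how much confounding misfiling leaves**

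This is also assumed throughout. Low resection is in 20% of target and 40% of comparator patients, R is 2 or 3, and the comparator is weighted to the target on recorded site alone. Recorded prevalence is s = p × sens + (1 − p)(1 − spec). The weighted comparator share is L = s_T × P(low | recorded rectal) + (1 − s_T) × P(low | not recorded rectal), with both probabilities taken in the comparator. The RR left is [1 + 0.2(R − 1)]/[1 + L(R − 1)].

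Worked case, sens 0.70 and spec 0.90:
- s_T = 0.14 + 0.08 = 0.22 and s_C = 0.28 + 0.06 = 0.34.
- L = 0.22 × 0.28/0.34 + 0.78 × 0.12/0.66 = 0.323.
- With R = 2, the RR left is 1.2/1.323 = 0.907.

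| Sens / spec | RR left, R = 2 | RR left, R = 3 | Confounding removed |
|---|---|---|---|
| No adjustment | 0.857 | 0.778 | 0% |
| 0.90 / 0.95 | 0.957 | 0.928 | about 70% |
| 0.70 / 0.90 | 0.907 | 0.851 | about 37% |
| 0.50 / 0.90 | 0.882 | 0.814 | about 19% |

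With prevalences reversed, the three adjusted rows become 1.049 to 1.078, 1.105 to 1.173 and 1.134 to 1.225. With equal prevalence there is no bias. The sketch ignores the other covariates, so it overstates what remains if they act as proxies.

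**6. Scale against precision**

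With 500 comparators at 3% (15 events) and 6,000 target patients at RR 1 (180 events), SE(log RR) = √(0.97/15 + 0.97/180) = 0.265. The 95% interval spans a factor of exp(1.96 × 0.265) ≈ 1.7 each way, before any loss from weighting.

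**The case against.** **Site and its proxies are already adjusted for.** This stands. The Rectum level, stoma on or before the index day, malignancy, approach, admission type and surgeon specialty are all in the model, and the stoma-stratified analyses are a further partial check. A reader might infer that low anterior resection goes unadjusted; the documents do not support that.

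**The site wording could mean the principal Table A-1 code of the index operation.** This is possible, since section 6.6.2 points to that table. The level for others does not prove that off-list primary codes are expected either: the left large intestine codes fit none of the three named sites. But section 8 leans towards the hospitalization's primary code, and on either reading a secondary rectal code beneath a primary sigmoid code is misfiled.

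**Repair codes do not contradict the objective.** This stands. The operations named in section 5.2 are examples, and entry also needs a circular-stapler charge. A reader might infer that repair patients are ineligible; the text does not say so. The number of repair-only patients is not given. The point concerns pooling without adjustment, not eligibility.

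**The limitation is disclosed.** It is, in section 8, but disclosure with an expectation of non-differential error does not remove residual confounding.

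**The bias is assumed and small beside the interval width.** Both parts are right. Small bias against wide intervals limits the urgency. It does not justify leaving recorded information unused.

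**Conclusion.** The point holds as a weakness of adjustment that should be mended before outcomes are analysed. The entry and site rules use different codes, operation type is outside the model, and no planned check can reveal the residual.

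Size and direction cannot be derived from the documents. The shifts of about 5% and 10% are arithmetic on an assumed 2.5-fold risk and assumed residual differences, and should not be read as an estimate of this study's bias. Bias in the RR needs a case-mix difference between devices, which the documents neither show nor exclude. Table 1 lists the Tri-Staple device in sizes 28 and 31 only, while both two-row families run from 21 to 33. That is a reason not to assume equal case mix, but not evidence of a difference.

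A reader might also infer that better coding would identify low anterior resection. It would not, because the Table A-1 categories carry no anastomotic height.

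**What to change.** 1. **Site (6.6.2).** Derive it from the Table A-1 codes dated on the index procedure day. Resection takes precedence over excision, and excision over repair; within the chosen operation type, take the most distal segment. The precedence stops a sigmoid resection with an incidental rectal repair from being filed as rectal. State which level the left large intestine codes take.
2. **Approach (6.6.2).** Read open versus laparoscopic from that same code, keeping the secondary robotic code and the Table A-6 conversion rule as they are.
3. **Propensity model (6.9.2) and balance tables.** Add operation type (resection, excision, repair) from the third character of the selected code.
4. **Sensitivity analysis (6.9.4).** Repeat the primary analysis without repair-only patients.
5. **Limitations (section 8).** State that anastomotic height is not coded, so low anterior resection is only partly captured, and that non-differential misclassification of site can still leave confounding.

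The cost is about 2 degrees of freedom in the propensity model, some derivation work and one extra analysis. No new data are needed. If a level is sparse among the roughly 500 comparators, the analyst who balances the data without outcome access can merge levels under a rule fixed beforehand.

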6.5 Dependent Variables (Outcomes)

Anastomotic leak within 30 days post-index procedure. AL will include all new AL cases identified during the index admission and those identified during a new admission within 30 days post-index procedure. A 30-day follow-up period is chosen as AL occurs at a median of 12 days (range, 3-30 days) after a colorectal procedure¹⁴ and it is the standard post-operation follow-up study period for most studies assessing AL after stapled anastomosis.

As there is no specific diagnosis code for AL in the International Classification of Diseases, 10th Revision, Clinical Modification (ICD-10-CM) taxonomy, the cumulative incidence of AL can only be estimated via either surrogate diagnoses or procedures which usually occur concomitantly with a leak, e. g., an abscess, peritonitis, a fistula or a post-index surgery stoma formation — a surgical treatment for severe AL.

As such, the presence of an ICD-10-CM diagnosis code for anastomotic leak surrogate diagnoses, such as fistula of intestine, peritonitis, or peritoneal abscess during the index admission or re-admission within 30 days post-index procedure, or the presence of an ICD-10-Procedure Coding System (ICD-10-PCS) procedure code indicating a diverting stoma occurred within 1-30 days post-index procedure will be used to define AL in the PHD. A similar approach was used in other studies assessing the risk of AL using electronic health records (EHR), such as PHD¹⁷ or Nationwide Inpatient Sample database¹⁸. The list of diagnosis codes is summarized in [Table A- 2](#), and the list of ICD-10-PCS codes indicating diverting stoma is summarized in [Table A- 3](#).

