Coagulation defects	D65, D66, D67, D68.0, D68.1, D68.2, D68.3%, D68.4, D68.5%, D68.6%, D68.9	Coagulation defects
Diabetes	E11.%, E10.%, E13.%, O24.%, E08.%, Z79.4, Z79.84	Diabetes mellitus, Gestational diabetes, Secondary diabetes, long term (current) use of insulin/oral antidiabetic drugs
Hypertension	I10, I11%, I12%, I13%, I15%	Hypertension
Immunodeficiency/immunosuppression	D80%, D81%, D82%, D83%, D84%	immunodeficiencies
	Z92.25	Personal history of immunosuppression therapy
	Z79.52	Long term (current) use of systemic steroids
	B20	AIDS/HIV
Kidney disease	N18%, N19, I12.0, I13.1%, N03.2, N03.3, N03.4, N03.5, N03.6, N03.7, N05.2, N05.3, N05.4, N05.5, N05.6, N05.7, N25.0, Z49.0%, Z94.0, Z99.2	Renal diseases
Malnutrition	E41, E42, E43, E44%, E46, E63%	Malnutrition, nutritional deficiencies
Obesity	E66.0%, E66.1, E66.2, E66.8, E66.9, Z68.3%, Z68.4%	Obesity, body mass index (BMI) 30-39, BMI 40 or greater

'%' at the end of the code denotes any value for subsequent characters.

RWE23-SAF-001:Comparative safety study to assess the risk of AL of 2-row vs 3-row circular staplers

Table A- 5: Diagnosis Codes (ICD-10-CM) for Indications of Surgery

PRIMARY DIAGNOSIS	CODE	CODE DESCRIPTION
Malignant neoplasms	C18.6	Malignant neoplasm of descending colon
	C18.7	Malignant neoplasm of sigmoid colon
	C18.8	Malignant neoplasm of overlapping sites of colon
	C18.9	Malignant neoplasm of colon, unspecified
	C19	Malignant neoplasm of rectosigmoid junction
	C20	Malignant neoplasm of rectum
Benign neoplasm	D12.4	Benign neoplasm of descending colon
	D12.5	Benign neoplasm of sigmoid colon
	D12.6	Benign neoplasm of colon, unspecified
	D12.7	Benign neoplasm of rectosigmoid junction
	D12.8	Benign neoplasm of rectum
Diverticular disease or Diverticulitis	K57.2%	Diverticulitis of large intestine
	K57.3%	Diverticular disease of large intestine
	K57.8%	Diverticulitis of intestine, part unspecified
	K57.9%	Diverticular disease of intestine, part unspecified
Intestinal obstruction	K56.2	Volvulus
	K56.6%	Other and unspecified intestinal obstruction

'%' at the end of the code denotes any value for subsequent characters.

Table A- 6: Diagnosis Codes (ICD-10-CM) for Conversion of Minimally Invasive Procedure to Open Procedure

CODE	CODE DESCRIPTION
Z53.31	Laparoscopic surgical procedure converted to open procedure
Z53.32	Thoracoscopic surgical procedure converted to open procedure
Z53.33	Arthroscopic surgical procedure converted to open procedure

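### Balance on the pooled diverticular level does not ensure balance between diverticulitis and diverticular disease, and no planned check would show a difference; any bias has unknown direction and is probably small

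*Supplement*

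**What the plan says.** Section 6.6.2 assigns the indication from the discharge coding: "Primary ICD-10-CM discharge diagnosis code recorded during the index hospital admission will be used to designate indication for surgery". It has five levels, and one of them is "Diverticular disease or Diverticulitis".

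Table A-5 in Appendix A places four code families under that level. K57.2% is described as "Diverticulitis of large intestine" and K57.3% as "Diverticular disease of large intestine"; K57.8% and K57.9% are the corresponding families with the part of the intestine unspecified.

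Section 6.9.2 lists among the propensity score variables the "procedural characteristics (procedure year, surgical site, primary diagnosis, surgical approach, and admission type". No other listed variable separates diverticulitis. The balance tables (B-2 to B-5, C-1 to C-8) and the incidence table B-6 carry only the pooled row.

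Section 6.5 defines leak by surrogate diagnoses, "such as fistula of intestine, peritonitis, or peritoneal abscess during the index admission or re-admission within 30 days post-index procedure", or by a diverting stoma on days 1 to 30. Table A-2 gives the diagnosis codes, including K63.2, K65.0 and K65.1.

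Two provisions bear on the point. Exclusion 3 in section 6.3 is headed "Presence of an admission diagnosis indicating anastomotic leak" and applies to Table A-2 diagnoses marked Yes in the present-on-admission field. Section 6.5 describes the outcome as new cases.

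**The concern.** Fistula, peritonitis and abscess can arise from diverticulitis itself. That is general clinical knowledge; the protocol does not state it. If the outcome codes are more frequent in diverticulitis than in diverticular disease, and one device is used in relatively more diverticulitis, the difference in mix would enter the relative risk as if it were a stapler effect.

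The planned checks would not show this. Section 6.9.2 chooses the weighting method by counting variables with an absolute standardized difference (ASD) above 0.10, and adds a variable to the log-binomial model only if it fails to balance. Both steps look at the pooled level, whose ASD can be near zero while its components differ. Section 8 expects outcome misclassification to be non-differential. For these codes, that expectation rests partly on a similar diverticulitis mix across devices, and nothing in the plan checks the mix.

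**Working it through.** **The plan's own figures.** The protocol gives no number for this point. Table 2 supplies the scale: 6,000 target and 500 comparator patients, comparator risk 2% or 3%, one-sided 0.025. The pooled-variance normal approximation for two proportions reproduces all six Table 2 powers to three decimals. For RR 2 at 3%:

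- Risks 0.06 and 0.03; pooled risk (360 + 15)/6,500 = 0.0577.
- Null SE = √[0.0577 × 0.9423 × (1/6,000 + 1/500)] = 0.01085.
- Alternative SE = √[0.06 × 0.94/6,000 + 0.03 × 0.97/500] = 0.00822.
- Power = Φ[(0.03 − 1.96 × 0.01085)/0.00822] = Φ(1.06) = 0.856, as stated.

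**Bias formula.** Suppose the stapler has no effect and all listed covariates are balanced. Let f be the share of patients with a diverticular indication, q the share of diverticulitis within them after weighting (q₁ in one cohort, q₀ in the other), and k the ratio of surrogate-outcome risk in diverticulitis to that in all other patients. Then

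spurious RR = [1 + f·q₁·(k − 1)] / [1 + f·q₀·(k − 1)].

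The documents give none of these inputs. Assumed: f = 0.3 to 0.5, k = 2 to 3, and q pairs 0.6/0.5, 0.6/0.4 and 0.7/0.4. The last column assumes that the present-on-admission exclusion removes 80% of the excess risk, so (k − 1) is multiplied by 0.2.

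| f | k | q₁ / q₀ | Ignoring the exclusion | 80% of excess removed |
|---|---|---|---|---|
| 0.3 | 2 | 0.6 / 0.5 | 1.18/1.15 = 1.03 | 1.036/1.030 = 1.01 |
| 0.4 | 3 | 0.6 / 0.4 | 1.48/1.32 = 1.12 | 1.096/1.064 = 1.03 |
| 0.5 | 3 | 0.7 / 0.4 | 1.70/1.40 = 1.21 | 1.140/1.080 = 1.06 |

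Swapping the cohorts inverts these values: 0.97 to 0.82 ignoring the exclusion, and 0.99 to 0.95 with it. If the two components are balanced, q₁ = q₀ and the factor is 1.00.

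Wider inputs (f up to 0.7, k up to 5, q₁ of 0.5 to 0.7 against q₀ of 0.4) give 1.03 to 1.40, the top value being 2.96/2.12. With 80% of the excess removed the range is 1.01 to 1.14, the top value being 1.392/1.224.

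**Against sampling error.** At RR 1 and Table 2's cohort sizes, the SE of the log RR is √[((1 − p)/p) × (1/6,000 + 1/500)], which is 0.265 at p = 3% and 0.326 at p = 2%. The unweighted 95% interval therefore spans a factor of exp(1.96 × 0.265) = 1.7 to exp(1.96 × 0.326) = 1.9 each way. By the method that reproduces Table 2, a wholly spurious RR of 1.05 would be called significant in the upper direction about 3% of the time, and one of 1.2 about 7% to 9%, against a nominal 2.5%.

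**The case against.** **The present-on-admission exclusion.** The most direct route is an abscess, peritonitis or fistula already there at admission, and section 6.3 is aimed at exactly that; section 6.5 adds that only new cases count. This stands, and it is why the lower range must be shown. It does not dispose of the point. The exclusion acts only on the flag value Yes. K57 codes are not in Table A-2, so patients with diverticulitis stay in the cohort unless they also carry a listed code. Nor can the exclusion address a higher postoperative risk of the same codes after diverticulitis.

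**Other covariates.** Admission type, surgical approach, surgical site and same-day stoma are in the score, and some plausibly track acute disease. This stands in part: a 20-point gap in mix remaining after weighting is a strong assumption. They are proxies, though, since diverticulitis may also be operated on electively.

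**Granularity is a judgement.** Every level of primary diagnosis pools unlike cases; malignancy, for example, merges colon and rectum. That is fair as a general remark. Here, however, the dividing line is already drawn in the code list, and it may separate patients by their risk of the outcome's own codes.

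**What a reader might wrongly infer.** It is tempting to conclude that residual confounding is present and will make the 2-row staplers look worse. The documents do not support that: they give no diverticulitis mix by device and no sign of which device would have more. It is also tempting to label K57.3%/K57.9% as disease without diverticulitis. Table A-5 does not say so; it shows no sub-codes, and % admits any subsequent characters.

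**Conclusion.** The point holds as a gap in resolution. The plan already treats indication as a confounder, but it adjusts and checks balance at a level that can hide a difference in mix between two listed code families.

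Whether such a difference exists is unknown, and the bias could exaggerate or mask a real effect. On assumed inputs the spurious RR is about 1.03 to 1.21 (or its inverse) ignoring the present-on-admission exclusion, and about 1.01 to 1.06 if that exclusion removes 80% of the excess risk; the 80% is itself an assumption. Against an interval spanning a factor of 1.7 to 1.9 each way, this is probably small. It does not affect the Table 2 power figures. The change is worth making because it is cheap and uses data already held, not because a material bias has been shown.

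**What to change.** In section 6.6.2 and Table A-5, split the level into K57.2%/K57.8% and K57.3%/K57.9%, labelled in Table A-5's own terms. Check the sub-codes before describing either level as without diverticulitis. Use both levels in the propensity model, in the ASD checks (Tables B-2 to B-5 and C-1 to C-8) and in Table B-6.

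No new data are needed. The cost is one more category in a score whose weighted group is small. The feasibility count in section 6.8 gives 526 left-sided cases for the Tri-Staple device. With an assumed 30% to 50% diverticular (526 × 0.3 = 158 to 526 × 0.5 = 263) and 40% of those diverticulitis, the smaller level would hold about 63 to 105 patients. It would be thinner still within the stoma strata of section 6.9.3, where the analysis is repeated and an extra level could make the weights less stable.
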